#### **10.4.3 General guidelines for reporting adverse events**

- All AEs, regardless of seriousness or relationship to IMP, spanning from the signature of the ICF until the end of the study as defined by the protocol for that patient, are to be recorded on the corresponding page(s) or screen(s) of the e-CRF.

- For this study, an endpoint assessment/adjudication committee is in place. This committee reviews important endpoints reported by the Investigators to determine whether the endpoints meet protocol-specified criteria. This is a periodic process, occurring after internal processing of the reported event (endpoint). The event as categorized by the Investigator will remain as such, even if judged differently by the adjudication committee later.
- Whenever possible, diagnosis or single syndrome should be reported instead of symptoms. The Investigator should specify the date of onset, intensity, action taken with respect to IMP, corrective treatment/therapy given, additional investigations performed, outcome, and his/her opinion as to whether there is a reasonable possibility that the AE was caused by the IMP or by the study procedure(s).
- The Investigator should take appropriate measures to follow all AEs until clinical recovery is complete and laboratory results have returned to normal, or until progression has been stabilized, or until death, in order to ensure the safety of the patients. This may imply that observations will continue beyond the last planned visit per protocol, and that additional investigations may be requested by the monitoring team up to as noticed by the Sponsor. At the prespecified study end-date, patients who experience an ongoing SAE or an AESI should be followed until resolution, stabilization, or death and related data will be collected.
- When treatment is prematurely discontinued, the patient's observations will continue until the end of the study as defined by the protocol for that patient.
- Laboratory, vital signs or ECG abnormalities are to be recorded as AEs if they are medically relevant based on the Investigator's medical judgement:
  - Symptomatic and/or
  - Requiring either corrective treatment or consultation, and/or
  - Leading to IMP discontinuation or modification of dosing, and/or
  - Fulfilling a seriousness criterion, and/or
  - Defined as an AESI

#### **10.4.4 Instructions for reporting serious adverse events**

In the case of occurrence of an SAE, the Investigator or any designees must immediately:

- ENTER (within 24 hours) the information related to the SAE in the appropriate screens of the e-CRF; the system will automatically send a notification to the monitoring team after approval of the Investigator within the e-CRF or after a standard delay.
- SEND (preferably by fax or e-mail) a photocopy of all examinations carried out and the dates on which these examinations were performed, to the representative of the monitoring team whose name, fax number, and email address appear on the clinical trial protocol. Care should be taken to ensure that the patient's identity is protected and the patient's identifiers in the clinical trial are properly mentioned on any copy of a source document provided to the Sponsor. For laboratory results, include the laboratory normal ranges.

- All further data updates should be recorded in the e-CRF as appropriate, and further documentation as well as additional information (for laboratory data, concomitant medications, patient status, etc) should be sent (by fax or e-mail) to the monitoring team within 24 hours of knowledge of the SAE. In addition, every effort should be made to further document any SAE that is fatal or life-threatening within a week (7 days) of the initial notification.
- A back-up plan (using a paper CRF process) is available and should be used when the e-CRF system does not work.

Any SAE brought to the attention of the Investigator at any time after the end of the study for the patient and considered by him/her to be caused by the IMP with a reasonable possibility, should be reported to the monitoring team.

#### **10.4.5 Guidelines for reporting adverse events of special interest**

For AESIs, the Sponsor must be informed immediately (ie, within 24 hours), as per SAE notification guidelines described in [Section 10.4.4](#), even if not fulfilling a seriousness criterion, using the corresponding screens in the e-CRF.

#### **10.4.6 Guidelines for management of specific laboratory abnormalities**

Decision trees for the management of certain laboratory abnormalities by Sanofi are provided in [Appendix D](#). The study population will be enrolled with preexisting impairment of renal function; rapid change in renal function of greater than **30% as compared** with the **mean of the prior 2 study visits** should be followed up as described in [Appendix E](#).

The following laboratory abnormalities should be monitored, documented, and managed according to the related flow chart in protocol appendices:

- Neutropenia
- Thrombocytopenia
- Increase in ALT
- Increase in creatine phosphokinase suspected to be of non-cardiac origin and not related to intensive physical activity
- Acute worsening of renal function (see [Appendix E](#))

In the event that the 'general guidance for the follow-up of laboratory abnormalities by Sanofi' [Appendix D](#) requires discontinuation of IMP, temporary discontinuation should be considered unless otherwise specified (please see [Section 10.3.1](#)).

#### **10.4.7 Guidelines for reporting events of special interest**

If an EOSI fulfills the criteria of an SAE, reporting should be performed according to the instructions for reporting of SAEs (see [Section 10.4.4](#)). Otherwise, reporting should follow the instructions for an AE (see [Section 10.4.3](#)).

Whenever AE data is collected or the patient reports DKA or intercurrent illness (including infections), generalized weakness, increased weight loss, GI symptoms including nausea, vomiting, or abdominal pain or other symptoms or signs that the Investigator believes may be consistent with DKA, the site will determine if an assessment for DKA, such as assessing blood beta-hydroxybutyrate level (BHB), is appropriate. If BHB or other laboratory testing confirms the presence of metabolic acidosis, then the “Possible DKA” e-CRF will be completed.

#### **10.4.8 Guidelines for reporting product complaints (investigational medicinal product)**

Any defect in the IMP must be reported as soon as possible by the Investigator to the monitoring team that will complete a product complaint form within required timelines.

Appropriate information (eg, samples, labels or documents like pictures or photocopies) related to product identification and to the potential deficiencies may need to be gathered. The Investigator will assess whether or not the quality issue has to be reported together with an AE or SAE.

### **10.5 OBLIGATIONS OF THE SPONSOR**

During the course of the study, the Sponsor will report in an expedited manner:

- All SAEs that are both unexpected and at least reasonably related to the IMP (SUSAR), to the regulatory authorities, IECs/IRBs as appropriate and to the Investigators.
- All SAEs that are expected and at least reasonably related to the IMPs to the regulatory authorities, according to local regulations.
- The following AESIs to those regulatory authorities who require such reporting:
  - Pregnancy
  - Symptomatic overdose with IMP
  - $ALT \geq 3$  ULN (if baseline  $ALT < ULN$ ) or  $ALT \geq 2$  times the baseline value (if baseline  $ALT \geq ULN$ ) (Please refer to related flowchart in [Appendix D](#)).

Adverse events that are considered expected will be specified by the reference safety information provided in the current IB.

If required, unblinding of SUSARs will be the responsibility of the Sponsor.

The Sponsor will report all safety observations made during the conduct of the trial in the CSR.

### **10.6 SAFETY INSTRUCTIONS**

#### **10.6.1 Severe hypoglycemia**

Severe hypoglycemia is an event requiring assistance of another person to actively administer carbohydrate, glucagon, IV glucose, or other resuscitative actions. These episodes may be associated with sufficient neuroglycopenia to induce seizure, unconsciousness, or coma. Plasma

glucose values may not be available during such an event, but neurological recovery attributable to the restoration of plasma glucose to normal is considered sufficient evidence that the event was induced by a low plasma glucose concentration. The definition of severe symptomatic hypoglycemia includes all episodes in which neurological impairment was severe enough to prevent self-treatment and which were thus thought to place participants at risk for injury to themselves or others.

**Note:** “requiring assistance of another person” means that the patient could not help himself or herself. Assisting a patient out of kindness, when assistance is not required, should not be considered a “requires assistance” incident.

Severe hypoglycemia will be reported as an AE. Additional information will be recorded including symptoms and/or signs, associated glucose value (if available), whether assistance was required and the treatment.

If the event fulfills SAE criteria, the severe hypoglycemia will also be reported as an SAE. For example, events of seizure, unconsciousness or coma must be reported as SAEs.

The definition of severe hypoglycemia is based on the American Diabetes Association workgroup on hypoglycemia classification (50, 51).

## **10.7 ADVERSE EVENTS MONITORING**

All events will be managed and reported in compliance with all applicable regulations and included in the final CSR.

## 11 STATISTICAL CONSIDERATIONS

### 11.1 DETERMINATION OF SAMPLE SIZE

The study is powered by primary endpoints of time to first occurrence of CV death or HHF in patients with LVEF <50%, and in the total patient population. In order to achieve the target number of events of 947 first occurrence of CV death/HHF in patients with LVEF <50% and 1341 first occurrences of CV death/HHF in the total patient population, it is estimated that approximately 4000 patients will be randomized over an estimated 29 months of recruitment period with approximately 3 months of follow-up after the last patient is randomized.

The sample size calculation is based on the following trial design assumptions:

- A recruitment period of approximately 29 months
- Approximately 3 months of follow-up after the last patient is randomized
- 29.2%, 39.7% and 44.5% event rate by Month 6, Month 12, and Month 24, respectively, in the placebo group (by assuming yearly hazard rate at Months 1, 2, 3, 4, 5, 6, 12, 24, and 36 be 1.06, 0.87, 0.74, 0.62, 0.49, 0.36, 0.32, 0.08, and 0.05, respectively)
- Hazard ratio (HR) = 0.81 for sotagliflozin versus placebo for patients with LVEF <50% and for patients with LVEF  $\geq$ 50%
- 2% annual censoring rate

This will provide:

- 90% power (with  $\alpha=0.05$ , 2-sided) to demonstrate superiority of the primary endpoint (first occurrence of CV death or HHF) comparing sotagliflozin versus placebo in patients with LVEF <50%.
- More than 90% power (with  $\alpha=0.05$ , 2-sided) to demonstrate superiority of the primary CV endpoint (first occurrence of CV death or HHF) comparing sotagliflozin versus placebo in the total patient population.

This is an event-driven study. Therefore, the study will continue until approximately 947 primary events (first occurrence of CV death or HHF) have been positively adjudicated in patients with LVEF <50%, AND approximately 1341 primary events (first occurrence of CV death or HHF) have been positively adjudicated in total patient population, and  $\geq$ 3 months follow-up for the last randomized patient.

Calculations were based log-rank test with user defined survival, accrual and drop-out rates by using EAST 6.4.

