|  | 

• hazard ratio (HR) = 0.81 for sotagliflozin versus placebo for patients with LVEF <50% and for patients with LVEF ≥50%

• 2% annual censoring rate

 
This will provide:
 

• 90% power (with <math>\alpha=0.05</math>, 2-sided) to demonstrate superiority for the primary endpoint (first occurrence of CV death or HHF) comparing sotagliflozin versus placebo in patients with LVEF <50%

• More than 90% power (with <math>\alpha=0.05</math>, 2-sided) to demonstrate superiority for the primary CV endpoint (first occurrence of CV death or HHF) comparing sotagliflozin versus placebo in the total patient population.

 
Analysis population:
 
The analysis population for primary and secondary efficacy endpoints will be the intent-to-treat (ITT) population that includes all randomized patients irrespective of compliance with the study protocol and procedures. Efficacy analyses will be conducted according to the treatment assigned at the Randomization Visit irrespective of the treatment received.
 
The safety analysis will be conducted on the safety population that includes all randomized patients who have received ≥1 dose of double-blind treatment. Safety analyses according to the treatment that the patients actually received.
 
Primary analysis:
 
The time to the first occurrence of CV death or HHF in patients with LVEF <50% will be analyzed by using stratified log-rank test with region (North America, Latin America, Western Europe, Eastern Europe, and rest of the world) as stratification factor. Stratified Cox proportional hazards model with region as stratification factor and treatment (sotagliflozin, placebo) as fixed effect factor will be used to provide the HR estimation between sotagliflozin and placebo along with its associated 2-sided 95% confidence interval (CI).
 
The time to the first occurrence of CV death or HHF in the total patient population will be analyzed by using stratified log-rank test with LVEF (<50%, ≥50%) and region (North America, Latin America, Western Europe, Eastern Europe, and rest of the world) as stratification factors. Stratified Cox proportional hazards model with LVEF (<50%, ≥50%) and region as stratification factors and treatment (sotagliflozin, placebo) as fixed effect factor will be used to provide the HR estimation between sotagliflozin and placebo along with its associated 2-sided 95% CI.
 
Kaplan-Meier curves of the cumulative incidence rate will also be provided by treatment groups.
 
All randomized patients (irrespective of whether they experienced efficacy event[s] or whether they permanently early discontinued double-blind treatment) will be followed from Randomization until their Follow-up Visit (or Study Closeout Visit, for patients who
 |

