## Secondary Hypotheses

- H3:** Total number (ie, including recurrent events) of CV death, HHF, or urgent HF visit in total patient population
- H4:** Time to CV death in patients with LVEF <50%
- H5:** Time to all-cause mortality in patients with LVEF <50%
- H6:** Time to first occurrence of the composite of positively adjudicated sustained  $\geq 50\%$  decrease in eGFR from Baseline (for  $\geq 30$  days), chronic dialysis, renal transplant, or positively adjudicated sustained eGFR <15 mL/min/1.73 m^2 (for  $\geq 30$  days) in total patient population
- H7:** Time to CV death in total patient population
- H8:** Time to all-cause mortality in total patient population

All tests will be two-sided. Significance levels  $\alpha_1 = 0.05$

( $\alpha_2 = \alpha_3 = \alpha_4 = \alpha_5 = \alpha_6 = \alpha_7 = \alpha_8 = 0$ ) are initially defined such that they sum up to  $\alpha = 0.05$ .

The procedure is as follows: Test the hypotheses  $H_i$ ,  $i=1, 2, \dots, 8$ , each at its local significance

level  $\alpha_i$ . If a hypothesis  $H_i$  can be rejected, reallocate its level to other hypotheses according to a pre-specified rule represented by the initial weighted graph. Update the reallocation weights in the reduced graph and repeat the testing step for the remaining, non-rejected hypotheses with the updated local significance levels. This possibility leads to further rejected null hypotheses with the updated local significance levels. The procedure is repeated until no further hypothesis can be rejected.

The reallocation of the local alpha levels is fully determined by the initial graph of the multiple testing strategy.

No further multiplicity adjustments will be made for other efficacy endpoints or subgroup analyses for which nominal p-values may be provided for descriptive purpose only.

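### The stated power of more than 90% for the total-population primary endpoint is a stand-alone figure; under the testing graph, the power to claim that endpoint is limited by the LVEF <50% test, about 90% at the target event counts

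*Protocol*

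**What the plan says.** Protocol section 11.1 assumes "Hazard ratio (HR) = 0.81 for sotagliflozin versus placebo for patients with LVEF <50% and for patients with LVEF" ≥50%, and sets targets of 947 first events in patients with LVEF <50% and 1341 in the total population. It then lists two powers in the same form, each at two-sided alpha 0.05: 90% for the LVEF <50% endpoint, and "More than 90% power" to demonstrate "superiority of the primary CV endpoint (first occurrence of CV death or HHF) comparing sotagliflozin versus placebo in the total patient population". The synopsis repeats the second line. Neither place says whether the figure takes account of the order of testing.

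Section 11.4.2.4 defines that order. "All tests will be two-sided". The whole 0.05 is placed on H1 (LVEF <50%), and H2 (total population) to H8 each start at zero. When a hypothesis is rejected, the rule is to "reallocate its level to other hypotheses according to a pre-specified rule represented by the initial weighted graph". The graph itself is not shown in the text available, so the weight on the edge from H1 to H2 cannot be read.

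**The concern.** H2 to H8 all start at zero, so H1 is the only hypothesis that can be rejected first. H2 cannot be claimed without H1, whatever the edge weights. The probability of claiming H2 is therefore at most the probability of rejecting H1, which the protocol puts at 90%. For H1 the single-test power and the power to make the claim are the same number. For H2 they are not, and listing both in one form hides the difference.

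What is at stake is how the design is read. Someone who takes section 11.1 alone would think that the total-population claim has the higher chance of success. Under the written rule it has a slightly lower chance than the LVEF <50% claim, and a miss on H1 blocks it even when the total-population result is strong.

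**Working it through.** **Inputs.** Hazard ratio 0.81 in both strata; 947 and 1341 events; two-sided 0.05 (section 11.1). 1:1 allocation (section 8.4). Initial alphas of 0.05 for H1 and 0 for H2 to H8 (section 11.4.2.4). Accrual, follow-up and dropout are not needed once the event counts are fixed.

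**Step 1: reproduce the plan's figures.** Schoenfeld's formula, with |ln 0.81| = 0.2107:

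- Events for 90% power: 4 × (1.960 + 1.282)² / 0.2107² = 946.5, rounded up to 947. This matches the protocol. Freedman's formula gives 954.
- H1: mean of Z1 = 0.2107 × √947 / 2 = 3.242; power = Φ(3.242 − 1.960) = 90.0%.
- H2 alone: mean of Z2 = 0.2107 × √1341 / 2 = 3.858; power = Φ(3.858 − 1.960) = 97.1%.

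Freedman's version gives 89.8% and 97.0%. Both printed statements reproduce as single-test powers.

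**Step 2: power to claim H2 under the graph.** This is P(Z1 > 1.960 and Z2 > c2), where c2 is the critical value at the level passed to H2. The LVEF <50% events are nested in the total, so the correlation is √(947/1341) = 0.840. The edge weight is unknown, so a range is shown:

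| Level at which H2 is tested | H2 alone | H2 claimed under the graph |
|---|---|---|
| 0.05 (all alpha passes) | 97.1% | 89.6% |
| 0.04 | 96.4% | 89.4% |
| 0.025 (half passes) | 94.7% | 88.7% |
| 0.01 | 90.0% | 86.1% |

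A simulation of 4 million draws gave 89.6% for the first row. In 97.1 − 89.6 = 7.5% of trials under the design assumptions, H2 would have p < 0.05 but could not be claimed because H1 missed.

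**Step 3: vary the event split.** The two targets are approximate and must both be met. Section 6.1.2 plans about 2900 of 4000 patients with LVEF <50%. If event rates are equal in the two strata (an assumption; no stratum-specific rates are given), 1341 total events imply 1341 × 2900/4000 = 972 events with LVEF <50%. Then the mean of Z1 is 0.2107 × √972 / 2 = 3.285, H1 power is 90.7%, and the correlation is √(972/1341) = 0.851. Power to claim H2 is 90.3% if all alpha passes and 89.4% if half passes.

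**Step 4: size of the gaps.** Against the printed 90%: 0.4 points (90 − 89.6) to 1.3 points (90 − 88.7) at 947 events; at 972 events, none if all alpha passes and 0.6 points if half passes. Against the stand-alone 97.1%: 7.5 to 8.4 points at 947 events, and 6.8 to 7.7 points at 972.

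**The case against.** The strongest reply is that section 11.1 makes no error. It gives its condition (alpha 0.05, two-sided) and its basis (a log-rank calculation in commercial software). Reporting power test by test is ordinary practice, and the figure is right on that basis. The 97% against which the larger gap is measured is not printed anywhere. Blocking H2 after a miss on H1 is openly stated in section 11.4.2.4. All of this stands. What remains is that the H2 line is not labelled as stand-alone, although it is worded as the power to demonstrate superiority, and the protocol allows that demonstration only through the graph.

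A reader might go further and infer that power above 90% is impossible under the written rule. The documents do not support that. The bound is the power of H1, and H1 has 90% only at 947 events. Both targets are approximate, both must be reached, and section 11.1 also requires at least 3 months of follow-up for the last patient. More than 947 LVEF <50% events may therefore be analysed, and at about 972 the printed words hold if all alpha passes.

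The SAP also limits the point. It takes precedence over the protocol (SAP 1.1), has a single primary objective in the overall population (SAP Appendix D), and states that the study is no longer powered for the original assumptions (SAP 1.3). SAP Appendix D refers to a protocol Amendment 2 that is not among the documents, so whether this power text was carried forward is unknown.

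**Conclusion.** The point holds as a labelling fault in the protocol's stated operating characteristics, and it is minor. The H2 figure is correct as a single-test power (about 97%), but the power to claim H2 under the graph is limited by the power of H1. At the target event counts that is about 89.6% if all alpha passes and 88.7% if half passes. Against the printed 90% the shortfall is about a point and can vanish if more LVEF <50% events accrue. Against the stand-alone figure it is about 7 points or more.

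That H2 depends on H1 follows from the printed initial alphas and needs no knowledge of the graph. The sizes rest on a hazard ratio of 0.81 in both strata, the event counts used, and at least half of H1's alpha reaching H2. A smaller weight would widen the gap: 86.1% if H2 were tested at 0.01.

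A reader might also infer that the trial was planned with too few events, or that the final analysis is affected. Neither follows. The 947 target gives H1 its stated 90%, and the SAP's analysis does not use this graph.

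**What to change.** In section 11.1 and the synopsis, reword the H2 line to say that power is about 97% for the stand-alone test at two-sided 0.05 with 1341 events. Add that under the graphical procedure H2 can be claimed only after H1 is rejected, so the power to claim it is limited by the power of H1, about 90% at the target event counts. The sponsor, who has the graph, can replace that limit with the exact value for the actual edge weight.

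The cost is a few words of protocol text and a slightly less favourable stated figure. Event targets, patient numbers and tests stay as they are, and the SAP needs no change on this account.
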